### 2.9.2 Analysis

All analyses on quality of life scores will be exploratory and will include all randomized patients.

#### 2.9.2.1 Determination of Assessment Times

The following will be the scheme to determining the time frame of a QOL assessment:

- 1) Baseline: Baseline evaluation is the QOL questionnaire collected closest, but prior to, the first day of starting study treatment/randomization;
- 2) Week 4 evaluation: If the QOL is assessed between week 1 and week 5
- 3) Week 8 evaluation: If the QOL is assessed between week 6 and week 10
- 4) Week 12 evaluation: If the QOL is assessed between week 11 and week 18
- 5) Week 24 evaluation: If the QOL is assessed between week 19 and week 30
- 6) Week 36 evaluation: If the QOL is assessed between week 31 and week 42

#### 2.9.2.2 Calculation of Compliance Rates

The following method will be used to calculate the compliance rates of QOL assessment. The compliance rate is calculated as the number of forms received out of the number of forms expected at each assessment point defined based on the following principles:

- 1) At baseline: the number of forms expected is the total number of patients who are eligible for the study and required to fill out QOL questionnaires.
- 2) FU period: the number expected at each assessment is the number of patients with baseline data minus the number of patients who have died or progressed during that and previous follow up period (with assessment window defined by 2.9.2.1).

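### The follow-up QOL compliance rule drops in-window progressors from the forms expected but not from the forms received, so read literally the rate can be inflated and can exceed 100%

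*SAP*

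**What the plan says.** SAP section 2.9.2.2 sets the rate in one sentence: "The compliance rate is calculated as the number of forms received out of the number of forms expected at each assessment point". For follow-up, the starting count is fixed by this clause: "the number expected at each assessment is the number of patients with baseline data". The rule then takes away everyone who has had an event by the close of the current window: "minus the number of patients who have died or progressed during that and previous follow up period". The period is tied to the QOL windows ("with assessment window defined by 2.9.2.1").

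Section 2.9.2.1 assigns a form to a visit by its date. The week 4 window is narrow ("Week 4 evaluation: If the QOL is assessed between week 1 and week 5"), and the week 8 window, covering weeks 6 to 10, is equally so. The later ones are wider: week 12 takes weeks 11 to 18, week 24 takes weeks 19 to 30 ("If the QOL is assessed between week 19 and week 30") and week 36 takes weeks 31 to 42. Each of these three ends six weeks after its nominal visit.

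Section 2.1 admits to the QOL analyses any patient with at least one assessment, at baseline or at follow-up. Section 2.9.2 makes all QOL score analyses exploratory.

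**The concern.** The subtraction covers the whole of the current window, including the part after the nominal visit. A patient who was due a form, returned it and then progressed before the window closed is not expected, yet her form has been received. No sentence keeps her in the denominator or takes her form out of the numerator.

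A smaller mismatch points the same way. The follow-up denominator starts from patients with baseline data, but section 2.1 foresees patients who have only follow-up forms. Those forms can be counted as received with no matching expected form.

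A ratio built this way is not a proportion. Compliance is what a reader uses to judge whether missing forms could undermine the comparisons of QOL change at each visit (section 2.9.2.3) and of the improved, stable and worsened categories (section 2.9.2.4). A rate that reads too high gives false reassurance, and one above 100% cannot be interpreted.

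**Working it through.** **Inputs from the SAP.** Median PFS is 10 months in both arms, with about 90 patients per arm, so 180 in total (section 1.2). The windows are those of section 2.9.2.1.

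**Assumptions that are not in the SAP.** PFS is exponential, every patient has baseline data, and every form is completed at the nominal week. True compliance c, among patients event-free at the nominal week, is not given; a range of 80% to 100% is used.

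**Check of the PFS model against the SAP's own figures.** The SAP states no compliance figure, so the check is on the design.

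- With 58 events per arm, the 90% CI factor is exp(1.645 × √(1/58 + 1/58)) = 1.357, and its inverse is 0.737. The SAP gives 1.36 and 0.74.
- With 12 months of uniform accrual and 12 months of follow-up, the probability of an event is 0.704. Then 58 / 0.704 = 82.3 per arm, and 82.3 / 0.90 gives 92 after rounding up. The SAP says approximately 90.

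The exponential 10-month model is therefore consistent with the SAP's planning.

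**Formula.** The hazard is ln 2 / 10 = 0.0693 per month, or 0.0693 / 4.348 = 0.01594 per week. With S(t) = exp(−0.01594 t), t in weeks:

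reported rate = c × S(nominal week) / S(window end) = c × exp(0.01594 × weeks from nominal visit to window end).

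| Visit | Window ends | Event-free at nominal week | Event-free at window end | Factor | Reported rate passes 100% if c exceeds |
|---|---|---|---|---|---|
| Week 4 | week 5 | 168.9 | 166.2 | 1.016 | 98.4% |
| Week 8 | week 10 | 158.4 | 153.5 | 1.032 | 96.9% |
| Week 12 | week 18 | 148.7 | 135.1 | 1.100 | 90.9% |
| Week 24 | week 30 | 122.8 | 111.6 | 1.100 | 90.9% |
| Week 36 | week 42 | 101.4 | 92.2 | 1.100 | 90.9% |

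The total of 180 cancels from the factor. At weeks 12, 24 and 36, a true 80% is reported as 88.0%, 90% as 99.0%, 95% as 104.5% and 100% as 110.0%.

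**Week 24 in detail.** Of 135.1 patients event-free when the window opens, 135.1 − 111.6 = 23.5 have an event within it. Of these, 122.8 − 111.6 = 11.2 have it after the nominal visit. These 11 or so were due a form and are then counted as not expected.

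**Sensitivity to form timing, same window, all forms returned.** If forms are completed as the window opens, the ratio is 135.1 / 111.6 = 1.21. At the nominal week it is 1.10. At the end of the window it is 1.00.

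**Choice of reference date for a repair.** If patients event-free at the window start were counted as expected, perfect completion at the nominal week would read 122.8 / 135.1 = 91%. That errs by a similar amount in the other direction.

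**The case against.** The strongest reply is that received forms *out of* expected forms naturally means a subset, so an analyst would count only forms from patients in the denominator and the rate could not pass 100%. That reading is possible, but the SAP does not state it. It would also leave out patients who were due a form and progressed later in the window, about 11 of 123 at week 24 in the illustration. Any forms they failed to return would then go unseen.

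The second reply is that the 1.10 depends on smooth exponential progression and on forms arriving at the nominal week. Progression is investigator-assessed by RECIST, so event dates follow the disease-assessment schedule, which the SAP does not show. This stands: the figures illustrate the size and do not predict it.

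A reader might infer three stronger claims that the SAP does not support:

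- **That the distortion keeps growing at later visits.** It does not. The factor depends only on the gap from nominal visit to window end, which is six weeks at weeks 12, 24 and 36 alike.
- **That it favours one arm.** It differs by arm only if the progression hazards differ, and the SAP plans on the same median in both.
- **That the QOL comparisons are themselves biased.** The change scores, the mixed model and the response categories do not use the compliance rate.

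It is also true that compliance is descriptive, supports an exploratory analysis and has no shell among Tables 1 to 24. That limits the severity.

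**Conclusion.** The point holds as a defect of definition. Followed literally, section 2.9.2.2 puts different patients in the numerator and the denominator, so follow-up compliance can be inflated and can exceed 100%. With exponential PFS at a 10-month median, complete baseline data and forms at the nominal week, the inflation is about 2% at week 4, 3% at week 8 and 10% (relative) at weeks 12, 24 and 36. The effect is smaller if forms come late in the window and larger if they come early. No separate size can be put on forms from patients without baseline data, because the SAP gives no count of them.

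The text does not establish that reported compliance will be inflated, since an analyst may match the two counts without being told to. Severity is minor.

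**What to change.** Replace the follow-up rule in section 2.9.2.2 with two statements:

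1. Forms expected at a visit are the patients with a baseline form who are alive and progression-free at the scheduled assessment date. The scheduled date should be named explicitly, and the window start should not be used.
2. Forms received at that visit are the forms dated within the section 2.9.2.1 window from those same patients.

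The numerator is then a subset of the denominator and the rate cannot exceed 100%. The change takes a sentence or two of the SAP and needs no new data. Its cost is somewhat lower reported compliance than the literal rule would give. The windows and all QOL score analyses stay as they are.

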#### 2.9.2.3 Cross-sectional analysis

The mean and standard deviation of QOL scores at baseline and mean and standard deviation of QOL change scores from baseline at each assessment time will be calculated. Then Wilcoxon Rank-Sum test is

used to compare two treatment arms in terms of change in QOL score at each assessment time from baseline.

Mean change in scores over time will be analyzed using generalized linear mixed model.

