## 2.3 Analysis Conventions

All comparisons between treatment arms will be carried out using a two-sided test at an alpha level of 5% unless otherwise specified. No formal adjustments will be made for the multiplicity of inferences for the other clinical endpoints.

Baseline stratification factors (excluding centre) that will be used to adjust the analyses where appropriate are listed below:

- Visceral metastases (yes versus no)
- duration of exposure to most recent endocrine therapy prior to randomization (4 groups)
  - duration  $\geq$  6 months versus  $<$  6 months in the advanced/metastatic setting
  - duration  $\geq$  24 months versus  $<$  24 months in the adjuvant setting
- Planned use of Fulvestrant versus Tamoxifen versus Aromatase Inhibitor (AI)

\*Add missing/unknown category whenever appropriate.

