#### 2.5.2.3 Response Rate and Clinical Benefit Rate

Response rates (percentages of CR/PR as best response) will be reported by treated arms for patients evaluable for response.

Clinical benefit rates (percentages of CR/PR/SD as best response) will be reported by treated arms for patients evaluable for response.

Response rates and clinical benefit rates will be compared between two arms using the Cochran-Mantel-Haenszel test adjusting for stratification factors at randomization (Table 16).

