### 2.9.2.4 QOL response analysis

QOL response is calculated as follows for a functional domain: A change score of 10 points from baseline was defined as clinically relevant. Patients will be assessed as improved if they have reported a score of 10-points or better than baseline at any time of the QOL assessment. Conversely, patients will be assessed as worsened if there is a reported score that is at least 10 points worse than baseline at any time of the QOL assessments without meeting the criteria for improved. Patients whose scores are intermediate between these values at every QOL assessment will be considered as stable. In contrast to functional domains, for the determination of patient's QOL response, classification of patients into improved and worsened categories is reversed for symptom domains and single items. A Chi-square test will be performed to compare the distributions of these three categories between two arms (improved, stable or worse).

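### The per-visit QOL comparison is a Wilcoxon test on raw change, which cannot use the baseline score or stratification factors, and the SAP does not say whether the mixed model includes them (minor).

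*SAP*

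**What the plan says.** Section 2.9.2.3 describes QOL by means and standard deviations at baseline and of change at each assessment. It then names a Wilcoxon rank-sum test, "used to compare two treatment arms in terms of change in QOL score at each assessment time from baseline". One further sentence covers the longitudinal analysis: "Mean change in scores over time will be analyzed using generalized linear mixed model". It lists no arm, visit, baseline or stratification term and no covariance structure.

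Section 2.3 has a general clause: "Baseline stratification factors (excluding centre) that will be used to adjust the analyses where appropriate are listed below". The factors are visceral metastases, duration of exposure to the most recent endocrine therapy (four groups) and planned endocrine partner (three options). QOL is neither named nor excluded there. For response and clinical benefit the SAP is explicit: section 2.5.2.3 has the rates "compared between two arms using the Cochran-Mantel-Haenszel test adjusting for stratification factors at randomization". Section 2.5.2.4 likewise adjusts the log-rank test for duration of response.

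On status, section 2.9.2 states: "All analyses on quality of life scores will be exploratory and will include all randomized patients".

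**The concern.** A change score subtracts the baseline value with a fixed coefficient of 1. When baseline and follow-up are imperfectly correlated, that coefficient is too large. The change score then keeps noise that regression on baseline would remove, and it stays negatively related to where the patient started. An arm that begins worse by chance will tend to look as if it improved more.

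The baseline score and the stratification factors are already collected, so the loss is avoidable. The rank-sum test cannot use them at all. The mixed model could, but two analysts could fit it differently and both comply with the SAP. What is at stake is the precision and interpretability of the QOL comparison, which serves one of the listed secondary objectives.

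**Working it through.** **Design figures.** The SAP gives no QOL sample size, SD, correlation or power. Its only design calculation (section 1.2) reproduces. With 58 events per arm the 90% limits are exp(±1.645 × √(1/58 + 1/58)) = 1.357 and 0.737, against the stated 1.36 and 0.74. With exponential PFS (median 10 months), 12 months of uniform accrual and 12 of follow-up, the event probability is 0.704. Then 58/0.704 = 82.3 per arm, and 82.3/0.90 = 91.5 with 10% dropout, close to the stated 90. I take 90 per arm below.

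**Assumptions not in the SAP.** Equal SD at baseline and follow-up; r from 0.3 to 0.8; SD 20 to 25 points (22 in the simulation); complete data on 90 per arm.

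**Precision.** Per patient, Var(change) = 2·SD²·(1 - r). After regression on baseline, the residual variance is SD²·(1 - r²). The ratio is 2(1 - r)/[(1 - r)(1 + r)] = 2/(1 + r), free of SD and sample size.

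**Imbalance.** For a realised baseline difference d between arms, the expected difference in change is the true effect minus (1 - r)·d. The last column uses d = 5 as an illustration.

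| r | Variance, raw change vs baseline-adjusted | Shift from a 5-point imbalance |
|---|---|---|
| 0.3 | 2/1.3 = 1.54 | 0.7 × 5 = 3.5 points |
| 0.5 | 2/1.5 = 1.33 | 0.5 × 5 = 2.5 points |
| 0.7 | 2/1.7 = 1.18 | 0.3 × 5 = 1.5 points |
| 0.8 | 2/1.8 = 1.11 | 0.2 × 5 = 1.0 point |

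The standard error of a baseline mean difference is SD × √(2/90): 3.0 at SD 20 and 3.7 at SD 25. A gap of 5 or more in either direction therefore has probability of about 9% to 18% for a given score under simple randomization.

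**The named test itself.** The variance ratio is for means, so the rank-sum test on change was also simulated against analysis of covariance (ANCOVA): normal scores, SD 22, 90 per arm, simple randomization, 3,000 runs per setting.

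| r | Power for an 8-point difference: rank-sum / ANCOVA | False-positive rate, all runs: rank-sum / ANCOVA | False-positive rate, baseline imbalance above 1.5 SE: rank-sum / ANCOVA |
|---|---|---|---|
| 0.3 | 50% / 71% | about 5% / 5% | 16% / 5% |
| 0.5 | 66% / 80% | about 5% / 5% | 14% / 6% |
| 0.7 | 86% / 93% | about 5% / 5% | 10% / 6% |

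The last column rests on the minority of runs with such an imbalance, so it is approximate.

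**Stratification factors.** Their contribution cannot be computed, because the SAP gives no association between them and QOL.

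**The case against.** The strongest reply is that the SAP labels QOL exploratory. No hypothesis, power or decision rule rests on it, and the trial is sized on the PFS hazard ratio. That stands and sets the severity. It does not remove the point: section 2.3 still applies ("All comparisons between treatment arms will be carried out using a two-sided test at an alpha level of 5% unless otherwise specified"), so the tests will be run and read.

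A rank test is also defensible for bounded scores, and the single-item formula in section 2.9.1.1 implies only a few possible values. The simulation used normal scores, so its power gap may not carry over to those items. This is a reason to keep the Wilcoxon tests as a check.

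Four stronger readings are tempting and are not supported:

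- A reader might infer that the mixed model omits baseline and strata. The SAP is silent on its covariates. A change outcome does not imply an unadjusted model, and section 2.3 may cover the stratification factors. The defect is that this is left open.
- A reader might infer that comparing change is biased. Over all randomizations it is unbiased and holds its level. The shift is conditional on the imbalance obtained, and a 5-point gap is possible but not typical. Minimization also makes large imbalance in the three factors themselves unlikely.
- A reader might set the 2.5-point shift against the 10 points in section 2.9.2.4 ("A change score of 10 points from baseline was defined as clinically relevant"). That section uses the figure to classify individual patients, so it is not a yardstick for a difference between arm means.
- A reader might add the number of scores and visits tested, or the loss of patients over time. Those are separate matters. The SAP openly leaves multiplicity unadjusted ("No formal adjustments will be made for the multiplicity of inferences for the other clinical endpoints"), and neither measures the harm from omitting baseline.

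**Conclusion.** The point holds as a minor one. The per-visit comparison is unadjusted by construction, and the SAP leaves the mixed model's adjustment unresolved. Under equal variances, the unadjusted mean-change comparison costs 11% to 54% more variance over r = 0.8 to 0.3. The upper end applies only if r is low; at r = 0.7 to 0.8 the penalty is 18% to 11%. In the randomization obtained, the estimate also carries (1 - r) of whatever baseline imbalance occurs. The values of r and SD are assumptions, and any gain from the stratification factors is unknown.

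**What to change.** In section 2.9.2.3, make the longitudinal mixed model the main between-arm QOL comparison and state its terms: arm, visit, arm-by-visit, baseline score, baseline-by-visit and the three stratification factors (excluding centre) as main effects, with a random patient effect. The outcome can be the score or the change from baseline; with baseline-by-visit in the model, the arm estimates are the same. Report the adjusted arm difference with its confidence interval at each visit and averaged over visits. Keep the Wilcoxon tests as a sensitivity or descriptive analysis, and keep the tabulated means and SDs of change.

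The cost is a few lines of SAP text and code, with no new data. The factors add six parameters (1 + 3 + 2), more if an unknown category is used. Patients without a baseline score cannot enter, but they cannot contribute to a change analysis now either.

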### 2.9.2.4 QOL response analysis

QOL response is calculated as follows for a functional domain: A change score of 10 points from baseline was defined as clinically relevant. Patients will be assessed as improved if they have reported a score of 10-points or better than baseline at any time of the QOL assessment. Conversely, patients will be assessed as worsened if there is a reported score that is at least 10 points worse than baseline at any time of the QOL assessments without meeting the criteria for improved. Patients whose scores are intermediate between these values at every QOL assessment will be considered as stable. In contrast to functional domains, for the determination of patient's QOL response, classification of patients into improved and worsened categories is reversed for symptom domains and single items. A Chi-square test will be performed to compare the distributions of these three categories between two arms (improved, stable or worse).

**3 Tables**

*Table 1 Accrual by centre*

Centre	Number of accrual (%)		
	Palbociclib 100mg N = ***	Palbociclib 125mg N = ***	Total N = ***
xxxx	XX (XX)	XX (XX)	XX (XX)

*Table 2: Accrual by Stratification Factors at Randomization*

Data set: All Randomized Patients			
	Number of patients (%)		
	Palbociclib 100mg N = ***	Palbociclib 125mg N = ***	Total N = ***
Visceral metastases			
Yes	** (**)	** (**)	** (**)
No	** (**)	** (**)	** (**)
Duration of exposure to most recent endocrine therapy prior to randomization			
≥ 6 months (advance)			
< 6 months (advance)			
≥ 24 months (adjuvant)			
< 24 months (adjuvant)			
Planned use endocrine			
Fulvestrant			
Tamoxifen			
Aromatase Inhibitor			

Source: Centralized Randomization File

Table 3: Treatment received

Actual treatment received	Number of accrual (%)		
	Palbociclib 100mg N = ***	Palbociclib 125mg N = ***	Total N = ***
Pal 100mg	XX (XX)	XX (XX)	XX (XX)
Pal 125mg			
No treatment			

Table 4: Eligibility status

Total patients allocated	Palbociclib 100mg N = ***	Palbociclib 125mg N = ***	Total N = ***
Ineligible	XX (XX)		
Total eligible patients	XX (XX)		
REASONS FOR INELIGIBILITY			
Reason 1	XX (XX)		
Reason 2	XX (XX)		
Major Protocol Violations			
	XXX		
	XXX		

Table 5: Summary of Follow-up

Data set: All Randomized Patients			
	Number of patients		
	Palbociclib 100mg N = ***	Palbociclib 125mg N = ***	Total N = ***
Median*	***	***	***
Min	**	**	**
Max	**	**	**

Median Follow-up based on inverse OS

*Table 6: Patient characteristics*

All randomized patients	Palbociclib 100mg N = ***	Palbociclib 125mg N = ***	Total N = ***
AGE			
<=39	XX (XX)		
40-49	XX (XX)		
50-59			
60-69			
>=70	XX (XX)		
Median (Range)	XX (XX)		
Q1, Q3			
Gender			
F			
Race			
Asian			
Black or African American			
etc			
ECOG PS			
0			
1			
2			
MENOPAUSAL STATUS			
As in meeting book			
Visceral metastasis (at baseline)			
Yes			
No			
Duration of exposure to most recent endocrine therapy prior to randomization (at baseline)			
≥ 6 months (advance)			
< 6 months (advance)			
≥ 24 months (adjuvant)			
< 24 months (adjuvant)			
Planned use of endocrine therapy (at baseline)			

Statistical Analysis Plan (SAP)

Doc. No.: MA.38  
 Version: V001  
 Date: 2018-08-08

Fulvestrant			
Tamoxifen			
Aromatase Inhibitor			
Histology			
Ductal			
Lobular			
ER status			
Negative			
Positive			
PR status			
Negative			
Positive			
Grade			
1			
2			
3			
Unknown			

Table 7. Baseline Hematology / Biochemistry

CTC AE 4.0 Hematology / Biochemistry table

Table 8. Baseline Non-Hematologic Adverse Event

CTC AE 4.0 Non-Hematologic Adverse Event table

Table 9. Baseline Concomitant Medication

All randomized patients	Palbociclib 100mg N = ***	Palbociclib 125mg N = ***	Total N = ***
Any baseline Concomitant Medication			
Yes	XX (XX)		
No	XX (XX)		

*Table 10. Log Rank and Cox Regression Model for PFS Survival*

Data set: All Randomized Patients				
	Univariate HR (95% CI)		Multivariate HR(95% CI) 	
Treatment (Arm 1 vs. Arm 2) (stratified)	***		--	
Treatment (Arm 1 vs. Arm 2) (un-stratified)				
ECOG PS (0 vs 1 or 2)				
Age (continuous)				
Histology (Ductal vs Labural)				
Grade				

(1) Based on Cox Model with all factors included.

*Table 11: PFS by Subsets*

Data set: All Randomized Patients			
	Number of patients (%)		
	Palbociclib 100mg N (# of events)	Palbociclib 125mg N (# of events)	HR (95% C.I.)
Visceral metastasis (at baseline)			
Yes	** (**)	** (**)	** (**)
No	** (**)	** (**)	** (**)
Duration of exposure to most recent endocrine therapy prior to randomization (at baseline)			
≥ 6 months (advance)	** (**)	** (**)	** (**)
< 6 months (advance)	** (**)	** (**)	** (**)
≥ 24 months (adjuvant)	** (**)	** (**)	** (**)
< 24 months (adjuvant)	** (**)	** (**)	** (**)
Planned use of endocrine therapy (at baseline)			
Fulvestrant	** (**)	** (**)	** (**)
Tamoxifen	** (**)	** (**)	** (**)
Aromatase Inhibitor	** (**)	** (**)	** (**)

*Table 12: PFS event Summary*

Data set: All randomized Patients		
	Number of Patients (%)	
	Palbociclib 100mg N = ***	Palbociclib 125mg N = ***
Patients with PFS event	*** (**)	*** (**)
Progression event	**	**
Death	**	**
Patients who were censored	*** (**)	*** (**)
Reason Censored		
No PFS event	**	**
Withdrawal of Consent	**	**

*Table 13. Log Rank and Cox Regression Model for Overall Survival*

Data set: All Randomized Patients				
	Univariate HR (95% CI)	Log-rank p-value	Multivariate HR(95% CI) 	Multivariate p-value
Same as PFS (table 10)	*** (*, *)	***	*** (*, *)	***
	*** (*, *)	***	*** (*, *)	***
	*** (*, *)	***	*** (*, *)	***
	*** (*, *)	***	*** (*, *)	***
	*** (*, *)	***	*** (*, *)	***
	*** (*, *)	***	*** (*, *)	***

(1) Based on Cox Model with all factors included.

*Table 15: Death Summary*

	Number of Patients (%)		
	Data set: All randomized Patients		
	Palbociclib 100mg N = ***	Palbociclib 125mg N = ***	Total N =
Patients who died			
Cause of Death			
Breast Cancer only			
Other primary malignancy			
Other condition or circumstance			
Patients who were censored			
Reason Censored			
Still Alive			
Withdrawal of Consent			

*Table 16: Response to Treatment*

	Number of Patients (%)		
	Data set: All treated patients with measurable disease		
	Palbociclib 100mg N = ***	Palbociclib 125mg N = ***	
Response to treatment			
CR	XX (%)	XX (%)	XX (%)
PR			
SD			
PD			

\*Stratification CMH test p-value for response rate:  $(CR+PR)/(CR+PR+SD+PD)$

\*\*Stratification CMH test p-value for clinical benefit rate:  $(CR+PR+SD)/(CR+PR+SD+PD)$

*Table 17: Duration of Response*

	Number of Patients (%)		
	Data set: All patients with CR/PR		
	Palbociclib 100mg N = ***	Palbociclib 125mg N = ***	Stratified p-value from log rank test
Duration of response			
Median	XX	XX	p-value =
Min	XX	XX	-
Max	XX	XX	-
Q1	XX	XX	-
Q3	XX	XX	-

*Table 18: Dose information*

Data set: All treated Patients: Cumulative dose (mg)			
	Number of patients		
	Palbociclib 100mg N = ***	Palbociclib 125mg N = ***	Total N = ***
Median	***	***	***
Min	**	**	**
Max	**	**	**
Q1			
Q3			

Cumulative dose (mg)

n

Mean

Std

Median

Min

Max

Q1

Q3

*Similar tables for*

*Daily dose(mg),*

*Dose intensity (mg/week)*

*Relative dose intensity (percent)*

*Cycle 1 and 2 dose intensity (mg/week)*

*Cycle 1 and 2 relative dose intensity (percent)*

90% or more dose intensity: N and percent

Data set: All treated Patients			
90% or more dose intensity: N and percent	Number of patients		
	Palbociclib 100mg N = ***	Palbociclib 125mg N = ***	Total N = ***
No	***	***	***
Yes	**	**	**

Cycle 1 and 2 90% or more dose intensity: N and percent

Data set: All treated Patients			
Cycle 1 and 2 90% or more dose intensity: N and percent	Number of patients		
	Palbociclib 100mg N = ***	Palbociclib 125mg N = ***	Total N = ***
No	***	***	***
Yes	**	**	**

*Table 19: Dose modifications*

Data set: All treated Patients			
At least one dose modification	Number of patients		
	Palbociclib 100mg N = ***	Palbociclib 125mg N = ***	Total N = ***
Yes	**	**	**
Reason of dose modifications Reason 1 Reason 2 ...			

Data set: All treated Patients			
At least done dose Reduction	Number of patients		
	Palbociclib 100mg N = ***	Palbociclib 125mg N = ***	Total N = ***
Yes	**	**	**
Reason of dose reduction Reason 1 Reason 2 ...			

Data set: All treated Patients			
Patients with dose discontinuation	Number of patients		
	Palbociclib 100mg N = ***	Palbociclib 125mg N = ***	Total N = ***
Yes	**	**	**
Reason of dose discontinuation			
Reason 1			
Reason 2			
...			

Table 20. Non-Hematology adverse events

CTC AE 4.0 Non-Hematology adverse events table

Table 21. Hematology / Biochemistry (Follow-up)

Hematology / Biochemistry table

Table 22. Serious Adverse Events

As in meeting book table.

Table 23. Off protocol treatment

Data set: All treated Patients			
Off treatment	Number of patients		
	Palbociclib 100mg N = ***	Palbociclib 125mg N = ***	Total N = ***
Cause1	***	***	***
2	**	**	**
3			
4			

*Table 24. Death on Trial*

Data set: All Randomized Patients			
Cause of Death	Number of patients		
	Palbociclib 100mg N = ***	Palbociclib 125mg N = ***	Total N = ***
Cause1	***	***	***
2	**	**	**
3			
4			

*Figure 1. KM plot for PFS*

*Figure 2. KM plot for OS*

*Figure 3. Cumulative incidence plot for grade 3 or 4 neutrophils*
